## **3. Study design**

### **3.1 Study types**

single-center, prospective, randomized, double-blind, controlled study

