### **6. Research process**

The experiment was carried out in Tongji Hospital, Tongji Medical College, Huazhong University of Science and Technology. For patient who were going to undergo laparoscopic partial hepatectomy, anesthesiologists went to the ward one day before surgery for preoperative evaluation, signed the informed consent form, and screened the subjects according to the inclusion and exclusion criteria. In according with the random results, the patients were randomly divided into ESPB group (experimental group) and TAPB&RSB group (control group). The patients were instructed to use analgesic pump and visual analogue scale (VAS). (Visual analogue scale (VAS): a 100 mm transverse line with 0mm at one end of the line indicates no pain, 100mm at the other end indicates severe pain and the middle part shows different levels of pain.)

1) All patients were routinely fasted before surgery, and no preoperative medication was given.

2) After entering the operation room, the patients in the experimental group and the control group took the sitting position, and the VAS scores of the patients in the resting state and the cough state were recorded. The subjects were scored preoperatively using the QoR-15 patient questionnaire (see supplementary).

3) Electrocardiogram, blood pressure, pulse, and blood oxygen saturation were monitored. After local anesthesia, ultrasound-guided internal jugular vein catheterization was performed, which could monitor central venous pressure (CVP) and record preoperative CVP after connecting the transducer.

4) The experimental group received ultrasound-guided ESPB, and bilateral ESPB was performed at T7 segment with 20ml 0.375% ropivacaine on each side. While the control group receives ultrasound-guided TAPB combined with RSB, which was performed under the costal margin with 10ml 0.375% ropivacaine for bilateral TAPB and 10ml 0.375% ropivacaine for bilateral RSB.

5) Anesthesia was induced with methylprednisolone 5mg, dexamethasone 5mg, penehyclidine hydrochloride 0.5 mg and palonosetron 0.25 mg, sufentanil  $0.5\mu\text{g}\cdot\text{kg}^{-1}$ , etomidate  $0.15\text{-}0.20\text{ mg}\cdot\text{kg}^{-1}$  and cisatracurium  $0.20\text{mg}\cdot\text{kg}^{-1}$ .

6) Tracheal intubation was performed after 5 minutes of mask oxygen inhalation; Ultrasound guided radial artery puncture catheterization was performed to monitor ambulatory blood pressure.

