7) Maintenance of anesthesia should use 1-2% sevoflurane inhalation, dexmedetomidine  $0.5\mu\text{g}\cdot\text{kg}^{-1}\cdot\text{min}^{-1}$  and fentanyl  $0.1\text{-}0.2\mu\text{g}\cdot\text{kg}^{-1}\cdot\text{min}^{-1}$ , and maintain blood pressure at baseline values of plus or minus 20%. In volume controlled ventilation mode, tidal volume was 6ml/kg, airway pressure was maintained within 25cmH2O, and end-tidal CO2 is maintained 35-45 mmHg. CVP values were recorded at 5, 10, 15, and 30min after nerve block. ECG, HR, BP, SpO2, CVP, PetCO2, BIS value, temperature, liquid intake and output are monitored during operation. Arterial blood gas analysis was used to correct acid-base imbalance and electrolyte imbalance.

8) Analgesic coherence: 30 minutes before the end of surgery, sufentanil 5ug was injected intravenously.

9) The patient was sent to PACU for observation for one hour after awake extubation, and then connected to an analgesic pump: sufentanil 15ug, nojan 15mg, palonosetron 0.3mg, 0.9% normal saline added to 150ml. The background infusion

rate was set according to the weight <50 kg at 1ml/h, 1.5ml/h for 50-60 kg and >70 kg at 2ml/h with a single compression dose of 2ml and a lockout time of 10min. According to the needs of patients, the analgesic pump could be pressed by themselves for analgesia. If pain cannot relieve (VAS>4 at rest), the remedial analgesia with a single dose of 2mg oxycodone can be used. At 1 hour after the end of surgery, recording the VAS scores of patients in resting and coughing states and the dose of analgesic pump. Asking patients if they had any adverse reactions, such as nausea, vomiting, pruritus, dizziness, headache, respiratory depression, etc.

10) After returning to the ward, patients could press the analgesic pump by themselves for additional analgesia. Lack of pain relief (VAS> 4 points) or, at the patient's request, rescue analgesia with a single dose of diclofenac sodium suppository. The dosage of analgesic pump, times of rescue analgesia, VAS scores in the resting and coughing and adverse reactions were recorded at 2h, 4h, 8h and 24h after operation. The QoR-15 patient questionnaire was used to evaluate the postoperative recovery at 24 hours after surgery.

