# **8.Data collection and statistical analysis**

## **8.1 Data collection**

Main observation indicator: consumption of morphine within 24 hours after surgery

Secondary observation indicators

- 1) Morphine consumption at 1h, 2h, 4h and 8h after surgery

- 2) Number of rescue analgesia at 1h, 2h, 4h, 8h and 24 hours after surgery
- 3) VAS scores in resting and coughing at 1h, 2h, 4h, 8h and 24h after surgery
- 4) CVP values at 5, 10, 15 and 30min after nerve block
- 5) QoR-15 patient questionnaire scores before and 24h after surgery
- 6) Postoperative liver function (the percentage increase of AST and ALT compare with preoperative), postoperative complications and discharge time

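### The pump background rate is not defined for eligible patients above 60 and up to 70 kg, and the rescue trigger does not match the VAS scale the protocol defines

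*Combined protocol and SAP*

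**What the plan says.** **Pump.** In Section 6, step 9, the pump follows the PACU stay: "The patient was sent to PACU for observation for one hour after awake extubation, and then connected to an analgesic pump". Its contents are "sufentanil 15ug, nojan 15mg, palonosetron 0.3mg, 0.9% normal saline added to 150ml". The background infusion is then given by weight: "rate was set according to the weight <50 kg at 1ml/h, 1.5ml/h for 50-60 kg and >70 kg at 2ml/h". Patients can add to it by pressing, "with a single compression dose of 2ml and a lockout time of 10min".

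**Eligibility.** Section 4.1 limits BMI to 19 to 28 kg/m² and sets no limit on body weight.

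**Endpoint.** Section 8.1 names the primary outcome: "Main observation indicator: consumption of morphine within 24 hours after surgery". Pump dose is recorded at 1 h (step 9) and at 2, 4, 8 and 24 h (step 10). The documents do not say whether background volume counts towards the endpoint.

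**Pain scale and rescue.** The opening of Section 6 defines the VAS as "a 100 mm transverse line with 0mm at one end of the line indicates no pain, 100mm at the other end indicates severe pain". The PACU rescue rule in step 9 reads: "If pain cannot relieve (VAS>4 at rest), the remedial analgesia with a single dose of 2mg oxycodone can be used". The ward rule in step 10 uses the same number, expressed in points, and also allows rescue whenever the patient asks for it. It does not say whether the resting or the coughing score applies, although both are recorded. Section 8.1 lists the number of rescue doses as a secondary outcome.

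**The concern.** The three weight bands do not join up. A patient of 65 kg falls in none of them, so whoever sets the pump must choose a rate that the protocol does not give. The background rate feeds the pump dose recorded at every time point, and 24 h consumption appears to be derived from that dose. An undocumented choice could therefore move recorded pump volume independently of the patient's demand, and a reader could not reproduce how these patients were treated.

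The rescue trigger has a similar fault on a smaller scale. A number without millimetres is applied to a scale defined in millimetres, and on the ward it is not tied to one of the two recorded scores. At stake there is the secondary count of rescue doses, which depends in part on when staff consider the threshold to be met.

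**Working it through.** No plan figure needs reproducing. The check is whether the bands cover all eligible weights, followed by simple arithmetic on volumes.

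**1. Coverage of the bands (Section 6, step 9)**

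| Weight | Background rate |
|---|---|
| below 50 kg | 1 mL/h |
| 50 to 60 kg | 1.5 mL/h |
| above 60, up to and including 70 kg | not stated |
| above 70 kg | 2 mL/h |

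Exactly 70 kg lies in the gap, because the top band starts above 70. The sentence shows no redaction or broken table.

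**2. Are patients in the gap eligible? (Section 4.1)**

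Weight = BMI × height², so height = √(weight / BMI).

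- 70 kg at BMI 28: √(70/28) = 1.58 m.
- 60 kg at BMI 19: √(60/19) = 1.78 m.

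Between these two heights every weight from 60 to 70 kg meets the BMI criterion. Outside them the overlap shrinks. The documents give no heights, so the following are assumed values:

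| Height | Weights allowed by BMI 19 to 28 | Part of that range in the gap |
|---|---|---|
| 1.45 m | 39.9 to 58.9 kg | none |
| 1.50 m | 42.8 to 63.0 kg | 3.0/20.2 = 15% |
| 1.65 m | 51.7 to 76.2 kg | 10/24.5 = 41% |
| 1.80 m | 61.6 to 90.7 kg | 8.4/29.1 = 29% |

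These are shares of the permitted weight range, not of patients.

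**3. Size of the difference between the neighbouring rates**

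Inputs: 1.5 and 2 mL/h; 150 mL reservoir; 2 mL per press; 10 min lockout. Pump time is taken as 23 h if the pump starts after the PACU hour, and as 24 h for the full window.

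- 24 h: 2 × 24 − 1.5 × 24 = 48 − 36 = 12 mL.
- 23 h: 2 × 23 − 1.5 × 23 = 46 − 34.5 = 11.5 mL.
- In presses: 12/2 = 6; 11.5/2 = 5.75.
- Share of the reservoir: 12/150 = 8%; 11.5/150 = 7.7%.
- Sufentanil at 15/150 = 0.1 µg/mL: 1.2 µg or 1.15 µg. This is one component only; the second listed analgesic component (15 mg in the same 150 mL) runs in the same proportion.
- For scale, pressing at every lockout gives 60/10 = 6 presses, or 12 mL, per hour. The whole 24 h background difference equals one hour of maximal pressing.

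All of these are gross differences, before any change in the patient's own pressing.

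**4. Rescue trigger against the defined scale**

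The line runs from 0 to 100 mm. Read literally, a trigger of 4 is 4/100 = 4% of its length. On an assumed 0 to 10 score it would be 4/10 = 40%. The documents state no conversion between the two.

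**The case against.** The best case against giving this much weight has four parts.

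- **Same rule, one site.** The trial is described as "single-center, prospective, randomized, double-blind, controlled study", and the pump rule does not depend on the arm. One settled local convention for the missing band is plausible. This stands, and it removes any claim of directional bias. It does not put the convention into the protocol.
- **Dose is captured anyway.** Pump dose is recorded at each time point whatever rate is set, and patients can press for more. This also stands: the gap creates no missing outcome data, and its net effect on consumption is unknown. The recorded total alone, however, does not show which rate was running.
- **It is an obvious slip.** Perhaps, but the text does not show whether a neighbouring band was meant to extend or a further band was lost. The reader cannot settle that.
- **Points suggests a 0 to 10 score.** That is a natural reading of the ward rule, and it makes the tenfold spread between readings look more like a notation slip than a real ambiguity. In addition, PACU rescue is permissive and ward rescue can be requested, so the threshold is not the only route to rescue. The mismatch with the defined line remains, as does the unspecified ward score, but this is the lesser part of the point.

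A reader might infer more than the documents support. The 12 mL is 33% of the lower background volume (12/36), but that is not a 33% effect on the primary endpoint: no consumption figure is given, the endpoint is expressed as morphine with no conversion from the pump drugs, and the counting of background is not stated. Nor can one say that a particular share of patients, or the centre of the trial population, falls in the gap, because the documents contain no weight or height data.

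**Conclusion.** Both passages are wrong as written, with modest impact. The background rate is undefined for weights above 60 and up to 70 kg. Patients of that weight are eligible at many adult heights, so a stated rule cannot be carried out for them. The neighbouring rates differ by 11.5 to 12 mL of solution over 23 to 24 h. The link to the primary endpoint is conditional on background infusion being counted. The rescue trigger does not fit the VAS as defined, and the ward rule does not name its score; this can affect the secondary rescue count.

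The text findings rest on no assumptions. The sizes rest on the assumed heights and on the 23 to 24 h pump time. No bias between arms, loss of power or number of affected patients is shown. The point is worth correcting because the correction costs little and makes opioid delivery, recorded pump dose and rescue counts traceable to a rule.

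**What to change.** The clinical team should:

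1. reconcile the weight bands in Section 6, step 9, so that every eligible weight maps to exactly one background rate;
2. make sure the rate actually set is recorded for each patient, so that background and patient-demanded volume can be told apart;
3. reconcile the rescue trigger in Section 6, steps 9 and 10, with the VAS as defined at the start of that section, using one unit throughout, and state whether the ward rule uses the resting or the coughing score.

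Which rate or threshold applies is a clinical decision, and none is proposed here. The cost is a wording amendment and at most one field on the case report form, if the form (which is not in the documents) does not already hold it. Sample size and analysis methods are unaffected.

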## **1. Research background**

According to the 2022 guidelines for perioperative care for liver surgery, implementing Enhanced Recovery After Surgery (ERAS) in liver surgery may improve postoperative outcomes. Compared with open hepatectomy, laparoscopic hepatectomy has the advantages of less postoperative hospitalization time and lower complication rates, which is recommended in well-trained teams and clinically appropriate situations. Postoperative pain after laparoscopic liver resection is composed of multiple factors, including somatic and visceral pain, which is caused by abdominal distension, laparoscopic port position and abdominal wall wounds. The peak pain of postlaparoscopic surgery mainly occurs in the first 24 hours, it is particularly significant to find an appropriate way to relieve pain.

Epidural analgesia has been the gold standard for perioperative pain control, but it is associated with longer hospitalization time and increased hospital costs and a higher incidence of urinary tract infections. Additionally, its use is limited by an increasing number of drugs that interfere with blood coagulation function. Regional anesthesia is an important component of multimodal analgesia, which can reduce the dosage of opioids after surgery, thereby reducing the occurrence of adverse reactions and it is helpful for postoperative recovery. Transversus abdominis plane block (TAPB) and Rectus sheath blocks (RSB) are widely used in abdominal surgery. TAPB blocks the sensory nerves of the anterolateral abdominal wall (T6-L1), and a Meta-analysis has shown that it is effective as epidural analgesia while having fewer episodes of hypotension. Bilateral rectus sheath blocks (RSB) was originally introduced to loosen the abdominal wall during surgery by blocking the terminal branches of the 9th, 10th and 11th intercostal nerves between the internal oblique and transversus abdominis muscles. It has now been shown to reduce opioid use and alleviate postoperative pain, but if the needle tip is too deep during RSB, it will have the risk of puncturing the abdominal organs. The limitation of both TAPB and RSB lies in their ability to provide somatic analgesia only without visceral analgesia.

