## **7. Possible risks and preventive measures**

### **7.1 Adverse event**

The investigators should faithfully fill in the adverse event recording form, record the time, severity, duration, measures taken and outcomes of adverse events. Explaining the criteria for the severity of adverse events, judging the relationship between adverse events and the trial drug was the 5-level classification standard (definitely related, possibly related, possibly unrelated, unrelated, and could not be determined). All adverse events should be traced until resolved properly or the patient's condition is stable.

Precautions for adverse events:

① Ultrasound-guided nerve block can visualize the puncture needle tips, effectively and greatly reduce the risk of local anesthetic poisoning and puncture injury.

② Local anesthetic poisoning: strict control the dose of drug, strict intraoperative monitoring. Once local anesthetic poisoning presents, it should be treated immediately according to the treatment procedure of local anesthetic poisoning, such as electrocardiogram monitoring, respiratory tract management, volume control, sedation and anticonvulsion, and the use of corresponding vasoactive drugs.

③ Puncture injury: Performing carefully and discreetly under visualization of ultrasound to ensure that tissue damage is minimized. Once present, surgery may intervene depending on severity.

Doctor will closely monitor your condition to ensure your health, and will truthfully tell you any changes in the course of the study and any newly identified adverse effects.

If you are harmed or have anything unexpected circumstances because of participating in this study, whether it is related to the intervention or not, your doctor will make a judgment and take medical action.

Physicians will try their best to prevent and treat possible harm as a result of this study. If an adverse event occurs during a clinical trial, a committee of medical experts will determine whether it is related to the intervention. Finally, according to the provisions of "Good Clinical Practice" in China, the sponsor will provide the cost of treatment and corresponding economic compensation for trial-related injuries.

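### Respiratory depression has no stated definition or objective postoperative measurement, and no study assessment is scheduled between 8 h and 24 h, so episodes may be missed and a reported zero could not be interpreted

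*Combined protocol and SAP*

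**What the plan says.** In section 6, step 9, the 1 h assessment includes: "Asking patients if they had any adverse reactions, such as nausea, vomiting, pruritus, dizziness, headache, respiratory depression, etc". Respiratory depression thus sits in the same patient-directed question as nausea and itching.

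Step 10 covers the ward period: "adverse reactions were recorded at 2h, 4h, 8h and 24h after operation". It does not say whether reactions are found by asking, observing, measuring or reading the chart, or what period each record covers.

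Oxygen saturation is named in step 3, before the block, and in step 7, in a list that ends "temperature, liquid intake and output are monitored during operation". No later step mentions SpO2, respiratory rate or sedation.

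On opioid exposure, step 9 describes a sufentanil pump with a weight-based background infusion and patient boluses. Step 10 continues it: "After returning to the ward, patients could press the analgesic pump by themselves for additional analgesia".

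Other provisions bear on the point. Step 9 gives a period of direct observation: "The patient was sent to PACU for observation for one hour after awake extubation". Section 7.1 sets a general duty: "The investigators should faithfully fill in the adverse event recording form", covering timing, severity, duration, action and outcome, with follow-up of every event. Section 7.2 requires serious events to be reported within 24 hours. The outcome list in section 8.1 names postoperative complications but not adverse reactions as such.

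**The concern.** Nausea, itching, dizziness and headache are symptoms, and the patient is the right source for them. Slow breathing or desaturation is a sign, and a sedated or sleeping patient cannot reliably report it. The only detection method that the plan states for respiratory depression is therefore unsuited to it, and for the ward records no method is stated at all.

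What is at stake is the meaning of the safety result. Section 1 justifies regional block partly because it can "reduce the dosage of opioids after surgery, thereby reducing the occurrence of adverse reactions", so a reader will look at the adverse reaction counts alongside opioid use. If respiratory depression has no definition and no measurement behind it, a reported zero has two explanations, that it did not occur or that it was not looked for, and the trial's records could not separate them.

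**Working it through.** The plan gives no figure for this harm (no event rate, no detection rate), so there is no stated number to reproduce. The check sets the provisions side by side, followed by one illustration on assumed values.

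**Schedule.** Postoperative contacts are at 1 h (step 9) and at 2, 4, 8 and 24 h (step 10). The longest interval is 24 − 8 = 16 h, and 16/24 = 0.67 of the first 24 h.

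**What each provision supplies for detecting respiratory depression**

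| Provision | Method stated | Objective respiratory record |
|---|---|---|
| Step 9, recovery-room stay | Observation for one hour, content not specified | None stated |
| Step 9, 1 h assessment | Asking the patient | None stated |
| Step 10, ward at 2, 4, 8, 24 h | Not stated | None stated |
| Section 7.1, adverse event form | How to document an event once known | None stated |
| Section 7.2, serious events | Reporting of events with listed consequences | None stated |

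Section 7.1 also promises close monitoring by the doctor, without method, frequency or data source. Section 7.2 depends on consequences such as death, disability or a longer stay, so an episode that was noticed and resolved without these need not enter by that route. No row supplies a definition of a case.

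**Illustration (assumed rates, not from the documents).** Let p be the true proportion of patients with an episode and s the proportion of episodes that are detected. With 60 patients (section 5), P(at least one recorded) = 1 − (1 − p·s)^60.

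| Assumed p | Expected true events, 60p | s = 100% | s = 50% | s = 25% |
|---|---|---|---|---|
| 1% | 0.6 | 45% | 26% | 14% |
| 2% | 1.2 | 70% | 45% | 26% |
| 5% | 3.0 | 95% | 78% | 53% |

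For example, at p = 2% and s = 50%, 1 − (1 − 0.01)^60 = 0.45. Incomplete detection makes a zero more likely, but the table says nothing about what s is under this plan.

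**Limit on what better detection can buy.** Section 5 plans 27 per group and 60 in total: 27/(1 − 0.10) = 30 per arm. With perfect detection and 0 events in 30, the one-sided 95% upper bound is 1 − 0.05^(1/30) = 9.5%. Complete ascertainment would therefore still leave the rate in each arm poorly determined.

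**The case against.** The strongest reply is that the listed times are scheduled recordings, not the only occasions on which an inpatient is seen. The duties in sections 7.1 and 7.2 are not tied to those times, the first hour after extubation is observed, and the 24 h record may look back over the preceding interval. The schedule is the same in both arms, and section 3.3 keeps follow-up staff blinded, so no bias between arms is shown. Sixty patients say little about this harm in any case.

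Much of this stands, and it rules out several stronger readings that a reader might infer:

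- That patients have no contact for 16 h. The documents support only that no study assessment is scheduled.
- That respiratory depression is sought by asking throughout, or that 8–24 h rests on recall. Asking is stated at 1 h only, and the ward method and recall period are not stated.
- That oxycodone adds to exposure on the ward. It is named in step 9, at the recovery-room stage; the ward rescue in step 10 is diclofenac.
- That the count will be near zero whatever happens, or that the safety committee would be misled by it. No rate is given, and section 7.3 refers to deaths and complications without naming this event.
- That the trial can no longer show fewer adverse reactions. The self-reportable ones are still collected at five times.

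What the reply does not meet is the absence of any definition, measurement or data source. A duty to document known events does not say how this one becomes known, and silence about the ward method is itself the gap.

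**Conclusion.** The concern holds as a weakness in safety measurement. The one detection method stated for respiratory depression, a question to the patient at 1 h, does not suit a sign that a sedated or sleeping patient cannot report. The ward method is unstated, no postoperative respiratory value is recorded, and 16 of the first 24 h (67%) contain no scheduled study assessment. Episodes may be missed, and a zero would be uninterpretable. The size of any under-count cannot be given: it depends on an event rate and a detection rate that the documents do not contain, and the table above rests on assumed values of both.

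The primary endpoint and the self-reportable reactions are not affected. The benefit of a change is a safety statement that can be interpreted; with about 30 per arm it is not the ability to compare arms on this event.

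**What to change.** - At the existing 1, 2, 4, 8 and 24 h contacts, record respiratory rate, SpO2 and a sedation score.
- At 24 h, abstract from the ward chart any respiratory values and respiratory events documented since 8 h. The documents do not say what the ward charts in that interval, so absent data should be recorded as missing, not as no event.
- Count respiratory depression from these records against an outcome definition that the investigators fix before enrolment.
- Add to section 8.1 the number of patients with each adverse reaction within 24 h, by arm, and report it descriptively. Testing each reaction at 0.05 would add several comparisons with no multiplicity rule and little power.

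The cost is a little more bedside recording at contacts already planned and one chart look-up per patient. It needs no new visits or staff. It changes measurement only, not patient care.
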